### **5.3 Lifestyle Considerations**

#### **5.3.1 Meals and Dietary Restrictions**

##### **5.3.1.1 Diet Restrictions**

Fasting requirements for laboratory safety evaluations are specified in Appendix 2.

###### **On Full PK Sampling Days (Days 1, 8 and 14)**

Participants will fast from all food and drinks, except water, for at least 8 hours prior to study drug administration until 1-hour postdose. Participants will fast from all food and drinks except water between study drug administration and the first scheduled meal. Meals and snack(s) will be provided by the investigator at time points indicated in the Schedule of Activities. Participants will fast from all food and drinks except water between meals and snacks. The caloric content and composition of meals will be the same on each full PK sampling day in each panel (for this study the meal content should be consistent within a given clinical site). After the 24-hour postdose procedures have been completed, subsequent meals and snacks will be unrestricted in caloric content, composition and timing.

Study intervention administration will need to be taken with water. Water will be restricted 1 hour and 1 hour after study intervention administration.

###### **On All Other Days**

Participants will fast from all food and drinks, except water, for at least 8 hours prior to study drug administration. Water will be unrestricted in timing. Meals and snacks will be unrestricted in caloric content, composition and timing.

##### **5.3.1.2 Fruit Juice Restrictions**

Participants will refrain from the consumption of grapefruit juice, grapefruits, and grapefruit products beginning approximately 2 weeks prior to administration of the initial dose of study drug, throughout the study and until the poststudy visit.

On full PK sampling days, participants will refrain from the consumption of all fruit juices 24 hours prior to and 24 hours after study drug administration.

On all other days during the study, the consumption of all fruits and fruit juices (except for grapefruit, grapefruit juices and grapefruit products) is allowed.

### **5.3.2 Caffeine, Alcohol, and Tobacco Restrictions**

#### **5.3.2.1 Caffeine Restrictions**

Participants will refrain from consumption of caffeinated beverages or xanthine-containing products from 12 hours prior to the prestudy and poststudy visits.

On full PK sampling days, participants will be permitted to consume approximately 2 units of caffeinated beverages or xanthine-containing products only between 1 hour and 2 hours postdose. Otherwise, participants will refrain from consumption of such products 8 hours prior to study drug administration until the last PK assessment is complete.

On all other days, caffeinated beverages or xanthine-containing products will be limited to no more than 6 units per day (1 unit = 120 mg of caffeine).

#### **5.3.2.2 Alcohol Restrictions**

Participants will refrain from consumption of alcohol 24 hours before the prestudy and poststudy visits. During the in-house period, consumption of alcohol is not allowed. At all other times, alcohol consumption is limited to no more than approximately 3 alcoholic beverages or equivalent servings (1 serving is approximately equivalent to: beer [354 mL/12 ounces], wine [118 mL/4 ounces], or distilled spirits [29.5 mL/1 ounce]) per day.

#### **5.3.2.3 Tobacco Restrictions**

Participants will follow the smoking restrictions (and if applicable, the use of nicotine/nicotine-containing products) defined by the CRU.

### **5.3.3 Activity Restrictions**

Participants will avoid unaccustomed strenuous physical activity (ie, weightlifting, running, bicycling, etc) from the prestudy (screening) visit until administration of the initial dose of study intervention, throughout the study (including washout intervals between treatment periods), and until the poststudy visit.

### **5.4 Screen Failures**

Screen failures are defined as participants who consent to participate in the clinical study but are not subsequently randomized in the study. A minimal set of screen failure information may be included, as outlined in the eCRF entry guidelines. Minimal information may include demography, screen failure details, eligibility criteria, and any AEs or SAEs meeting reporting requirements.

Participants may be rescreened as appropriate, per Section 8.10.1.

## 5.5 Participant Replacement Strategy

If a participant discontinues from study intervention or withdraws from the study a replacement participant may be enrolled if deemed appropriate by the investigator and Sponsor. The replacement participant will generally receive the same intervention or intervention sequence (as appropriate) as the participant being replaced. The replacement participant will be assigned a unique treatment/randomization number.

The replacement participant may begin dosing at the subsequent dose level for that panel, based on investigator and Sponsor review and discussion.

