If applicable, participants will be washed off their current antipsychotic therapy. The washout may start with a down titration of the antipsychotic treatment during the screening phase per direction of the investigator. Participants should not receive antipsychotics for at least 5 days or 3 half-lives (whichever is longer) prior to Day 1. For longer half-life antipsychotics (eg, aripiprazole and brexpiprazole), if deemed appropriate by the investigator, a participant may stop treatment (ie, cessation of atypical antipsychotic therapy) as an outpatient, but should be confined to the clinical research unit within a week of stopping treatment and minimally beginning on Day -5. Antipsychotic SOC may be restarted following the assessments that occur 72-hours following the last dose of study drug. At the investigator's discretion, the participant may be domiciled for a longer duration i.e., participants may be domiciled prior to Day -5 or for a longer period following end of study treatment while SOC is restarted.

Where applicable (Dose Regimen 2 or 3), titration to the next dose level within a regimen will occur per the investigator's medical discretion based on the tolerability of study intervention within an individual participant. If the investigator deems it necessary, dose titration within an individual may be paused temporarily for the duration of any tolerability issues (i.e., AEs) and resumed when deemed appropriate. Any changes to the dose regimen will not prolong an individual's participation in the trial and therefore it is acknowledged that failure to adhere to the protocol-defined dose regimen may result in some participants not reaching the escalation targets. Participants may be down-titrated by the investigator at any time without consultation of the Sponsor in the case of safety or tolerability issues.

Regardless of the state of the dose escalation of each participant it is important to keep participants in the study as the data collected at all doses is valuable for the purposes of defining a clinical tolerability margin. Any changes to the protocol specified treatment regimen will be documented in a Protocol Clarification Letter.

Figure 2 Study Design Diagram

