Following completion of 14 days of dosing in at least 6 participants, a decision to enroll an additional 8 participants in the current panel and enroll participants in a more conservative dose regimen (per [Figure 2](#)) will be made jointly by the investigator(s) and Sponsor. Dose regimen decisions will be based on the review of adverse event data. The Dose Regimen selected will be documented in a Protocol Clarification Letter.

Because this is a Phase 1 assessment of MK-8189 in humans, the PK, pharmacodynamic, and safety profiles of the compound are still being elucidated. This protocol is therefore written with flexibility to accommodate the inherent dynamic nature of Phase 1 clinical studies.

Refer to Section 8.10.6 for examples of modifications permitted within the protocol parameters.

Specific procedures to be performed during the study, including prescribed times and associated visit windows, are outlined in Section 1.3 of the SoA. Details of each procedure are provided in Section 8.

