## 6 STUDY INTERVENTION

Study intervention is defined as any investigational intervention(s), marketed product(s), placebo, or medical device(s) intended to be administered to a study participant according to the study protocol.

Clinical supplies, study intervention(s) provided by the Sponsor, will be packaged to support enrollment and replacement participants as required. When a replacement participant is required, the Sponsor or designee needs to be contacted before dosing the replacement participant. Clinical supplies will be affixed with a clinical label in accordance with regulatory requirements.

Global clinical supply complaints and/or temperature excursions are to be reported to the Clinical Complaints Intake mailbox, via email to [[contact]](mailto:[contact]), within 1 business day of awareness.

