## **6.6.1 Stopping Rules**

### **6.6.1.1 Study Stopping Rules**

The following stopping rules will be used during the conduct of this study.

If any of the below stopping rules are met, the study will be paused, and no further dosing will occur until the Sponsor has reviewed the totality of data available. To continue the study (on joint agreement with the Sponsor and investigator), an amendment will be submitted for approval.

- Three or more MK-8189 treated participants per Panel (Dosing Regimen) meet any of the criteria listed under 6.6.1.2 and the clinical investigator judges the event to be related to MK-8189.

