### 9.4 Analysis Populations

The following populations are defined for the analysis and reporting of data. All participants will be reported, and their data analyzed, according to the treatment(s) they actually received.

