#### 9.4.2 Per-Protocol (PP) Population

The Per-Protocol Population consists of the set of data generated by the subset of participants who comply with the protocol sufficiently to ensure that these data will be likely to exhibit the effects of treatment, according to the underlying scientific model. Compliance covers such considerations as exposure to treatment, availability of measurements and absence of

important protocol deviations. Important protocol deviations will be identified to the extent possible prior to unblinding by individuals responsible for data collection/compliance, and its analysis and interpretation. Any participants or data values excluded from analysis will be identified, along with their reason for exclusion, in the CSR. At the end of the study, all participants who are compliant with the study procedure as aforementioned and have available data from at least one treatment will be included in pharmacokinetics analyses.

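### Section 5.5 optionally lets an active replacement in Panel B or C start above the panel's first titration step

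*Combined protocol and SAP*

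**What the plan says.** Section 5.5 allows a participant who discontinues or withdraws to be replaced, and sets a default: "The replacement participant will generally receive the same intervention or intervention sequence (as appropriate) as the participant being replaced". It then adds an option: "The replacement participant may begin dosing at the subsequent dose level for that panel, based on investigator and Sponsor review and discussion". Section 6 adds a procedural safeguard: "the Sponsor or designee needs to be contacted before dosing the replacement participant".

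Section 4.1 and Table 2 give the regimens. Panel A takes 24 mg from Day 1. Panel B takes 16 mg on Days 1 to 3 and 24 mg from Day 4. Panel C takes 8 mg on Day 1, 16 mg on Day 2 and 24 mg from Day 3. In Regimens 2 and 3, Section 4.1 makes each step up a matter for the investigator, "based on the tolerability of study intervention within an individual participant". The within-participant departures it describes are pausing the titration and titrating down.

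For the choice between regimens, Section 4.1 states: "Dose regimen decisions will be based on the review of adverse event data".

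**The concern.** The three regimens differ only in their first three days, so the early titration is what Panels B and C exist to test. An active replacement who starts one level up has not had that titration, yet occupies a place in the panel.

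Two things are at stake. The first is individual safety: the replacement reaches the higher dose with no personal experience of the lower one, which is the condition Section 4.1 attaches to a step up. This matters most if Panel B was opened because the first cohort did not tolerate Regimen 1, since the option would then allow a Panel B replacement to begin at the very dose that prompted the change. The second is interpretation: the panel's adverse-event review is meant to show how its titrated start is tolerated, and this participant cannot contribute to that. Section 2.1 says that the study's data will support dose selection for Phase 3.

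**Working it through.** **Inputs.** Panel sizes are from Table 2 and Section 9.8 (12 active, 4 placebo). First-cohort size and ratio (8 participants, 3:1) and the dose sequences are from Section 4.1.

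**1. The plan's own total.** 3 panels × (12 + 4) = 48, which matches the Synopsis. A first cohort of 8 at 3:1 gives 8 × 3/4 = 6 active.

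**2. Who the option can affect.** Section 4.1 uses the idea of a next dose level for the titration steps of Regimens 2 and 3. Panel A has no second level and placebo has no dose level. That leaves active replacements in Panels B and C.

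**3. What is skipped.** Section 5.5 does not say how many days a late starter is dosed. Purely as an illustration, assume a full 14 days:

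| Sequence | Sum | Total |
|---|---|---|
| Regimen 1 (Panel A) | 24 × 14 | 336 mg |
| Panel B as planned | 16 × 3 + 24 × 11 | 312 mg |
| Panel B, first step skipped | 24 × 14 | 336 mg, same as Regimen 1 |
| Panel C as planned | 8 + 16 + 24 × 12 | 312 mg |
| Panel C, first step skipped | 16 + 24 × 13 | 328 mg, no listed regimen |

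If only the panel's remaining days were dosed, the totals would be 24 × 11 = 264 mg over 11 days (Panel B) and 16 + 24 × 12 = 304 mg over 13 days (Panel C). The starting dose is the same either way, and the point rests on the starting dose alone. Section 5.5 also does not say what the subsequent level is counted from. If it is counted from the level at which the replaced person stopped, a Panel C replacement could skip both 8 mg and 16 mg. Each workable reading skips at least the first step.

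**4. Against the rule for stepping up.** Under Section 4.1, a step up depends on how that same participant has tolerated the drug, and the changes it describes hold or lower the dose. The note under Table 2 likewise speaks only of downward adjustment. The option in Section 5.5 goes up, without that individual experience. It does not breach the cap in Section 8.10.6, because 24 mg is the protocol maximum.

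**5. Share of the evidence.** One skip is:

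- full panel: 1/12 = 8.3% of active participants, or 1/13 = 7.7% if the replaced person is also counted;
- first cohort: 1/6 = 16.7%, or 1/7 = 14.3% on the same basis.

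**6. Possible effect on the adverse-event rate.** If the higher start carried d percentage points more early risk, one skip would move the expected panel rate by d/n. The documents give no value for d, so the range below is an assumption and includes zero:

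| d (points) | n = 6 | n = 12 |
|---|---|---|
| 0 | 0 | 0 |
| 20 | 3.3 | 1.7 |
| 40 | 6.7 | 3.3 |

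In people, that is 0 to 0.4 extra participants with an event. The plan sets no numerical tolerability threshold, so none of these values can be shown to change a decision.

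**The case against.** The case for leaving the sentence alone is fair, and much of it stands.

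- **It is an exception under control.** The default is the same sequence, and use of the option needs investigator and Sponsor review. Those parties also make the regimen decisions (Sections 4.1 and 6.6), by clinical review of events rather than by a pooled rate. They would know who started higher, and Section 4.1 has regimen changes recorded in a Protocol Clarification Letter.
- **The higher start may do no harm.** Section 4.3.1 reports that a 24 mg start was well tolerated in schizophrenia, with no discontinuations for treatment-related events and no severe events. Tolerability in bipolar I disorder is what this study is to establish, so zero excess is possible but not shown.
- **Mixed sequences are already accepted.** Section 4.1 foresees pauses and down-titration. Those, however, respond to a participant's own tolerability and do not raise the starting dose.
- **The first-cohort case is less likely.** Section 4.1 allows the decision once at least 6 participants have completed 14 days, so a cohort of 8 can lose two without replacement.
- **The analysis rules help.** Section 9.4 analyses people "according to the treatment(s) they actually received", and for the per-protocol set Section 9.4.2 says "Compliance covers such considerations as exposure to treatment, availability of measurements". Neither restores the missing evidence on the titrated start.

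Two stronger readings are tempting, and the documents do not support either.

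A reader might infer that a skip would distort the study pause rule, which is triggered when "Three or more MK-8189 treated participants per Panel (Dosing Regimen) meet any of the criteria listed under 6.6.1.2". The criteria in Section 6.6.1.2 describe worsening of bipolar illness, not the acute tolerability events (such as extrapyramidal symptoms and vomiting) that concern the regimen decision. Nothing in the documents ties a titration step of one to three days to those criteria, and counting such a person toward a safety pause is cautious.

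A reader might also infer a material bias in the Day 1 PK means. Under assumed dose proportionality, one skip multiplies the geometric mean by r^(1/n). For Panel B (r = 24/16 = 1.5) that is +7.0% at n = 6 and +3.4% at n = 12. For Panel C (r = 16/8 = 2) it is +12.2% and +5.9%. With an assumed geometric CV of 30% to 50%, the upper 95% limit, exp(t·s/√n) − 1 with s = √ln(1 + CV²), already lies 20.5% to 35.0% above the mean at n = 12, and 36.1% to 64.2% at n = 6. The shift is within sampling error, PK is exploratory (Section 3), and regimen decisions use adverse events. If the replacement joined at a later panel day, there would be no Day 1 sample to shift.

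**Conclusion.** The point holds as a minor one. Section 5.5 permits an active replacement in Panel B or C to start above the panel's first titration step, without the individual-tolerability condition that governs a step up elsewhere. That participant says nothing about the titrated start. This follows from the wording of Sections 4.1 and 5.5 and needs no statistical assumption.

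The consequence is small: each skip takes one active participant out of the evidence on the titrated start, with the shares shown above. It arises only if Panel B or C opens, an active participant is replaced, and the option is used. The documents do not support a claim that a regimen decision would change, or that adverse-event rates would rise by any particular amount. The individual-safety reason for closing the gap stands without such a claim.

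**What to change.** Replace the sentence in Section 5.5 that contains the option with: *Replacement participants start at Day 1 of the panel's dose regimen.* Pausing and down-titration under Section 4.1 remain available to replacements as to everyone else.

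The cost is one sentence and slightly less flexibility in filling a panel. Sample size and Section 9 do not change. The edit does not settle how paused or down-titrated participants are grouped in the safety tables; that is a separate matter.

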## 6 STUDY INTERVENTION

Study intervention is defined as any investigational intervention(s), marketed product(s), placebo, or medical device(s) intended to be administered to a study participant according to the study protocol.

Clinical supplies, study intervention(s) provided by the Sponsor, will be packaged to support enrollment and replacement participants as required. When a replacement participant is required, the Sponsor or designee needs to be contacted before dosing the replacement participant. Clinical supplies will be affixed with a clinical label in accordance with regulatory requirements.

Global clinical supply complaints and/or temperature excursions are to be reported to the Clinical Complaints Intake mailbox, via email to [[contact]](mailto:[contact]), within 1 business day of awareness.

### 6.1 Study Intervention(s) Administered

The study intervention(s) to be used in this study are outlined in [Table 1](#).

Country-specific requirements are noted in Appendix 7.

Table 1 Study Interventions

Arm Name	Arm Type	Intervention Name	Intervention Type	Dose Formulation	Unit Dose Strength(s)	Dosage Level(s)	Route of Administration	Regimen/ Treatment Period/ Vaccination Regimen	Use	IMP or NIMP/ AxMP	Sourcing
Active	Experimental	MK-8189	Drug	Tablet	4 mg 12 mg	All dose levels	Oral	Dose Regimens 1, 2 and 3	Test Product	IMP	Provided centrally by the Sponsor
Placebo	Placebo Comparator	Placebo	Drug	Tablet	0 mg	All dose levels	Oral	Dose Regimens 1, 2 and 3	Placebo	IMP	Provided centrally by the Sponsor

IMP=investigational medicinal product; NIMP/AxMP=noninvestigational/auxiliary medicinal product.

The classification of IMP and NIMP/AxMP in this table is based on guidance issued by the European Commission and applies to countries in the EEA. Country differences with respect to the definition/classification of IMP and NIMP/AxMP may exist. In these circumstances, local legislation is followed.

All supplies indicated in [Table 2](#) will be provided per the “Sourcing” column depending on local country operational requirements. If local sourcing, every attempt should be made to source these supplies from a single lot/batch number where possible (eg, not applicable in the case where multiple lots or batches may be required due to the length of the study, etc).

Refer to Section 8.1.8 for details regarding administration of the study intervention.

All placebos were created by the Sponsor to match the active product.

## **6.2 Preparation/Handling/Storage/Accountability**

### **6.2.1 Dose Preparation**

There are no specific calculations or evaluations required to be performed to administer the proper dose to each participant. The rationale for selection of doses to be used in this study is in Section 4.3.

### **6.2.2 Handling, Storage, and Accountability**

The investigator or designee must confirm appropriate temperature conditions have been maintained during transit for all study intervention received, and any discrepancies are reported and resolved before use of the study intervention.

Only participants enrolled in the study may receive study intervention, and only authorized site staff may supply or administer study intervention. All study interventions must be stored in a secure, environmentally controlled, and monitored (manual or automated) area in accordance with the labeled storage conditions with access limited to the investigator and authorized site staff.

The investigator, institution, or the head of the medical institution (where applicable) is responsible for study intervention accountability, reconciliation, and record maintenance (ie, receipt, reconciliation, and final disposition records).

For all study sites, the local country Sponsor personnel or designee will provide appropriate documentation that must be completed for drug accountability and return, or local discard and destruction if appropriate. Where local discard and destruction is appropriate, the investigator is responsible for ensuring that a local discard/destruction procedure is documented.

The study site is responsible for recording the lot number, manufacturer, and expiry date for any locally purchased product (if applicable) as per local guidelines unless otherwise instructed by the Sponsor.

The investigator shall take responsibility for and shall take all steps to maintain appropriate records and ensure appropriate supply, storage, handling, distribution, and usage of study interventions in accordance with the protocol and any applicable laws and regulations.

